9.3 Randomisation

Randomisation will be as per section 11.5 of the platform protocol. Randomisation will be on a 1:1 basis to arthroplasty or internal fixation, stratified by recruitment centre. The allocation sequence will be generated by the trial statistician. Full details will be stored in a separate randomisation and blinding plan stored in the confidential statistics section of the trial master file.

Randomisation will be performed as close to the start of surgery as possible to avoid the risk of postponement of surgery or moving to a different theatre list.

9.4 Blinding

This will be a pragmatic study so that the treating clinical team cannot be blinded to the treatment allocation. The outcome data will be collected from participants and entered onto the study central database by a research assistant in the study central office to reduce the risk of assessment bias. The participants in this comparison will not be informed which of the two treatments they have received. No formal assessment of the success or otherwise of the blinding will be made.

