7.4.2 Secondary

In addition to the common outcome instruments, described in the master protocol, objective mobility and pain will also be collected:

Objective mobility: The Short Physical Performance Battery (SPPB) at 6 weeks will provide an objective measure of mobility and physical performance.

The SPPB is a multi-component test instrument for assessing mobility in older adults, scoring ability in chair rise speed, walking speed, and timed balance tests.⁹ Each test performance is given a 0-4 ordinal score, based on extensively validated cut-points. A zero score indicates the participant tried but was unable, or the assessor or participant deemed it unsafe to attempt it, or the participant was unable for other health reasons. This means that, unlike most physical capacity tests, even the frailest study participants, for example those with cognitive impairment, can still register a meaningful score. Scores from the three tests are summed, resulting in SPPB scores from 0 to 12. The SPPB developers have produced detailed guidance on the testing procedures, enabling reliable application in the hospital, homes and other care settings. The SPPB will be administered by a member of the research team.

In order to check the fidelity of the administration of this instrument, sites will be required to submit two video recordings of the SPPB. The first recording will be of a practice session, during site training, and feedback will be given to the team following this session. The second recording will be of the first assessment with a participant. Verbal consent for this video recording will be obtained from the participant at the beginning of the recording. The trial team will assess the fidelity of the SPPB using an agreed checklist defined within a trial specific instruction.

Pain: Participants or their proxy will report the pain verbal rating scale (VRS), a five responses ordinal scale (1-5) measuring pain;¹⁰ responses are labelled "no pain," "slight pain," "moderate pain," "severe pain," and "unbearable pain" where 1 indicates "no pain" and 5 "unbearable pain". It has been validated in patients with hip fracture with good response rates, including from patients with cognitive impairment; it is reliable and sensitive in this patient group.

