8.1.2 Main phase

During the main comparison phase, patients will be recruited for a further 29 months from a minimum of 25 additional centres, bringing the minimum number of recruitment centres to 40 across the UK.

Participants will be allocated on a 1:1 basis to either fixation or hip replacement treatments. Both of these treatments are routinely used within the NHS. Clinical teams across the NHS are very familiar with both treatments.

Assessments will include all those described in the Master protocol, augmented with additional data relevant to this specific randomised comparison. In summary:

Baseline demographic data will be collected as per the requirements in the master protocol (see section 12.2). When the patient is discharged from hospital, the local research team will check the participant medical records for any early complications.

At 6 weeks post-diagnosis, the majority of patients with this injury are routinely followed up in clinic (this may be face-to-face or virtual). Participants will be asked to complete the EQ-5D-5L⁸ and answer questions about their mobility, pain and residential status. At this time the SPPB test⁹ will be performed by a member of the local research team. For those patients unable to attend hospital, this assessment will be made at the participant's (care) home.

In addition to the data being collected at 4 months post-diagnosis to satisfy the platform outcomes (see master protocol), a pain verbal rating scale (VRS) will be collected. This same combination of questionnaires will be collected at 12-months post-diagnosis. Additionally, at 12 months a second review of medical notes will allow for the collection of further complications and contacts with the treating hospital. Routinely obtained radiographs relating to the hip fracture up until 12 months post-diagnosis will be collected.

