9.6.2 Visits and Contacts

Contact 1: Details of the baseline contact are described in the Master Platform Protocol.

Contact 2: All participants will be invited for face to face or remote follow-up for a routine clinical checkup at approximately 6 weeks post-surgery. It is expected that approximately 60-70% of patients will be able to attend this appointment, with the remaining patients unable to as they are either still in a hospital setting or due to cognitive impairment and/or mobility. For those patients attending hospital a member of the local research team will perform the SPPB test with the patient and ask them to complete the required questionnaires. A 'mobile' research associate will visit those patients unable to attend, at their current place of residence to complete the SPPB test and questionnaires.

Contacts 3-8: Further follow-ups at 4, 12, 24, 36, 48 and 60 months post-diagnosis, will be completed with the participant or a proxy either via telephone interviews by a member of the central research team, or through electronic means depending on choice expressed by the participant or proxy at the time of consent/declaration. All de-identified routinely acquired radiographs up until 12 months will be collected and transferred to the central study team.

Event-driven contact: Reporting of an expected and related, local SAE (a related local complication - as defined in Section 10.1 of this appendix) by either the site staff, participant or proxy, will trigger collection of additional EQ-5D assessments. For participants yet to complete the first 4 months of data collection this will be a single additional EQ-5D report recorded by the site staff or participant/proxy as soon as possible after the event has been reported. For participants who have completed 4 months of data collection, this will be the index EQ-5D report (at the time of the event report) and two subsequent reports 4 and 8 weeks later.

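### Section 9.4's central-office safeguard against assessment bias does not protect the 6-week SPPB, which local or mobile research staff score face to face with no stated assessor blinding

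*Protocol*

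**What the plan says.** Section 9.4 of the protocol makes three statements that bear on this point.

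- Clinicians: "the treating clinical team cannot be blinded to the treatment allocation".
- Participants: "The participants in this comparison will not be informed which of the two treatments they have received".
- Outcome data: "The outcome data will be collected from participants and entered onto the study central database by a research assistant in the study central office", with the stated aim of lowering assessment bias.

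The section adds that the success of blinding will not be formally assessed. It does not mention the local research team or the SPPB assessor.

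The 6-week visit is described elsewhere. Section 8.1.2 says the SPPB "will be performed by a member of the local research team". Section 9.6.2 agrees: "For those patients attending hospital a member of the local research team will perform the SPPB test with the patient". It expects 60-70% to attend and sends a mobile research associate to the rest. Table 1 gives the 6-week setting as face to face, in clinic or at home. Section 8.1.2 also says that, at discharge, "the local research team will check the participant medical records for any early complications".

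Section 7.4.2 describes the scoring. Each of three tests scores 0 to 4 against validated cut-points. Zero is given, among other reasons, where "the assessor or participant deemed it unsafe to attempt it". Each site submits two videos, one of a practice session and one of its first participant assessment, to check fidelity of administration.

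**The concern.** Section 9.4 names one measure against assessment bias, and that measure is absent where an assessor has most influence on a score. The SPPB is the outcome for secondary objective 2, is presented as the objective measure of mobility, and is the only performance test in the schedule.

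Cut-points for timed tasks limit discretion, but two openings remain: how much encouragement the assessor gives, and whether a task is judged unsafe and scored zero. Both could be influenced by knowing whether the hip was fixed or replaced, for example if the assessor believes one construct is sturdier. Such an influence would act in the same direction across participants and would not average out.

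A reader of 9.4 would conclude that this risk had been dealt with. Because blinding is not to be assessed, the trial would also have no data to show whether it had been.

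**Working it through.** **1. The passages side by side**

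| Time point | Who obtains the data | Does central collection apply? |
|---|---|---|
| 6 weeks, SPPB | Local research team, or mobile associate (8.1.2, 9.6.2) | No |
| 6 weeks, questionnaires | Answered by participant or proxy; requested by the same staff (9.6.2, Table 1) | No, but answers are not assessor-scored and participants are not told their allocation |
| 4 months onward, including the primary EQ-5D-5L | Central team by telephone, or electronically (9.6.2) | Yes |

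**2. What the assessor may know.** The local team checks medical records at discharge (8.1.2). Table 1 draws treatment details up to discharge from medical records and the therapist. Operation details go into the study CRF (9.5.3), with no one named as entering them. So the team that supplies the SPPB assessor has access to the operative information. The protocol does not say whether the same individual reviews the notes and does the test, or what the mobile associate is told.

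**3. Other controls.** The videos cover one practice session and one participant per site, and check fidelity. They do not bear on knowledge of allocation.

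**4. Illustration of size.** The protocol gives no figure for SPPB power or bias, so there is nothing of its own to reproduce on this point. The inputs are:

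- Number assessed: 263 per arm, borrowed from section 11.1. That figure is the primary-outcome requirement, and it reproduces: the normal approximation for a difference of 0.085, SD 0.3 and 90% power gives 262, the t-test version 262.7, so 263. It is not an SPPB number, because 11.1 counts deaths as scored outcomes.
- SPPB SD: assumed 3, range 2.5 to 3.5.
- Bias: assumed shift b between arms of 0.25 or 0.5 point, with no true difference.
- Share exposed: 60-70%, the expected clinic attenders.

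Formulas: SE = SD × √(2/263); mean shift s = b × share; false-positive rate = Φ(s/SE − 1.96) + Φ(−s/SE − 1.96).

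With SD 3, SE = 3 × 0.0872 = 0.262. For b = 0.5 and share 0.6, s = 0.30, s/SE = 1.15, and the rate is about 0.21.

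| SD | b = 0.25, share 0.6 / 0.7 | b = 0.5, share 0.6 / 0.7 |
|---|---|---|
| 2.5 | 10.6% / 12.6% | 28.0% / 36.2% |
| 3.0 | 8.8% / 10.3% | 20.9% / 26.7% |
| 3.5 | 7.8% / 8.8% | 16.6% / 20.9% |

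If every assessment were exposed, including those by the mobile associate, the ranges would be 13-21% for 0.25 point and 37-63% for 0.5 point.

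**The case against.** The best defence of 9.4 is grammatical. The central-office assistant may be the one who enters the data, with collection left open, and then 9.4 does not strictly conflict with 8.1.2 and 9.6.2. That reading is possible, but it does not rescue the safeguard: entering a score centrally cannot protect a test already scored at the bedside.

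Assessor procedures may also sit in documents not shown: the randomisation and blinding plan (9.3), the trial-specific instruction for the SPPB checklist (7.4.2) or the Master Protocol. This stands as a limit. One cannot say that no safeguard exists, only that this protocol states none and that 9.4 is wrong for this visit as written.

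A reader might infer more than the text supports:

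- **That the assessor knows the operation, or abstracted it.** The protocol has the local team check notes for early complications. It does not say that this person completes the operation form or performs the SPPB. The supportable wording is that the assessor may know.
- **That the 6-week questionnaires are equally exposed.** Local staff ask for them, but participants or proxies answer, and participants are not told their treatment. For self-report, that is the relevant protection, and 9.4 provides it.
- **That the false-positive figures are estimates.** They follow correctly from their inputs, but the SD and bias sizes are assumed and the sample size is borrowed. Timed tasks with fixed cut-points may leave less room for bias than the shifts used.

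**Conclusion.** The point holds in a limited form. Section 9.4 offers a protection against assessment bias that the design does not give to the 6-week SPPB, and no passage says the SPPB assessor is kept unaware of allocation.

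The effect is confined essentially to one secondary outcome at one visit. The primary outcome, EQ-5D-5L at 4 months, is collected centrally or electronically as 9.4 describes, and the sample size of 878 does not depend on this.

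No size can be derived from the protocol. Under the stated assumptions, shifts of 0.25 and 0.5 point among clinic attenders would give false-positive rates of about 8-13% and 17-36% against a nominal 5%. These show only that a modest shift could matter. The correction should be made, but the trial's main conclusion does not rest on it.

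**What to change.** 1. In 9.4, limit the central-office statement to the centrally collected contacts from 4 months onward, and state that the 6-week SPPB is assessed by local or mobile research staff.
2. Where existing staffing allows, have the SPPB done by a team member who did not review that participant's operation record and who scores the test before viewing notes or radiographs. Do not give the mobile associate the allocation. Where a site has only one researcher, the test goes ahead and awareness is recorded.
3. Add one CRF item: was the assessor aware of the operation performed, yes or no. Amend the 9.4 sentence on not assessing blinding so that the two agree.
4. Report the SPPB as not assessor-blind unless that item supports a stronger description.

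The cost is protocol wording, a line in the SPPB instruction and one CRF item, with no extra staff because the separation applies only where current staffing permits. The downside is minor rota inconvenience, and small sites will be recorded as unblinded.

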9.5 Description of the randomised treatments

Clinical Research Protocol Template version 15.0 CONFIDENTIAL © Copyright: The University of Oxford and Oxford University Hospitals NHS Foundation Trust 2019 Page 17 of 27

9.5.1 Preoperative assessments

Participants will usually be assessed in the Emergency Department. Diagnosis of a hip fracture will be confirmed by a plain radiograph, as per routine clinical care. Supplementary imaging will be at the discretion of the treating clinical team. Routine investigations, anaesthetic assessment, antibiotic and venous thromboembolic prophylaxis will be used as per local policy.

9.5.2 Anaesthetic technique

A regional or general anaesthesia technique will be used for every participant as per routine clinical care. Intra-operative analgesia may be achieved by combining a local anaesthetic nerve block using either a nerve stimulator or ultrasound-guided technique, IV paracetamol 1g intravenous infusion and opiate analgesia as clinically indicated. Details of the anaesthetic technique will be recorded in the study CRF.

9.5.3 Surgical treatment

All participants will receive perioperative prophylactic antibiotics in accordance with current protocols agreed at each centre. Appropriate preparation, positioning and anaesthetic technique will be left to the discretion of the clinical team as per their normal clinical practice. Resources related to delivering treatment in both arms will be collected in study case report forms, including type of intervention received, admission and discharge date, complications and further treatments required. Participants will be randomly allocated to one of the treatment arms:

INTERNAL FIXATION

Internal fixation is usually performed using either a sliding hip screw or cannulated screws, with a recent trial showing no difference in outcome.¹⁴ We will take a pragmatic approach, allowing surgeons to follow their usual practice for internal fixation.

Intraoperative fluoroscopy will be used to confirm that the fracture has not significantly displaced. The fracture will be fixed in-situ with no attempt to manipulate the fracture by closed or open means. Fixation will be achieved using a technique and implant chosen by the operating surgeon.

HIP REPLACEMENT

One of two types of hip replacement may be offered to people with hip fractures - hemiarthroplasty and total hip arthroplasty (THR). Patient position, surgical approach, implant and surgical technique will be chosen by the operating surgeon.

Details of the operation will be recorded in the study CRF.

9.5.4 Early post-operative care

All participants will be under the care of a multi-disciplinary team with input from a physician with an interest in hip fracture.

After surgery, key aspects of initial rehabilitation will be standardised; all participants will:

- 1. be encouraged to fully weight bear, and
- 2. attempt mobilisation on the day of, or first day after, surgery with a therapist.^{7 15}

The local multi-disciplinary team will be responsible for delivering rehabilitation and managing onward referral and discharge planning as per usual practice, according to local care pathways.

Clinical Research Protocol Template version 15.0 CONFIDENTIAL © Copyright: The University of Oxford and Oxford University Hospitals NHS Foundation Trust 2019 Page 18 of 27 The intensity and content of rehabilitation sessions provided within the acute hospital and in other inpatient settings or the community will be according to individual needs of the participant, within local resources. Details of this rehabilitation will be recorded in the study CRF.

9.6 Assessments

9.6.1 Schedule of assessments

The overall schedule of assessments, including the common outcome set and the additional outcomes measured for this comparison, and methods for data collection are described in the table below:

Time Point	Data	Source	Setting
Baseline	 i) Demographics ii) Relevant medical history iii) Injury details Pre-injury: iv) EQ-5D v) Residential status vi) Subjective mobility status vii) Resource use 	Participant or proxy & medical record	Acute inpatient - face to face; medical record review
Up to point of discharge	 i) Treatment details including: a) Initial mobilisation details* b) Rehabilitation details* ii) Resource provision iii) Early complications 	Medical records & therapist	Acute inpatient; Medical record review
6 weeks post- diagnosis*	i) EQ-5D ii) SPPB iii) Pain VRS iv) Complications v) Residential status vi) Subjective mobility status	Participant or proxy	Outpatient clinic OR domiciliary visit - face to face
4 months post-diagnosis	 i) EQ-5D ii) Pain VRS* iii) Complications iv) Residential status v) Subjective mobility status vi) Resource use 	Participant or proxy & medical record	Telephone, online or postal
12 months post- diagnosis*	 i) EQ-5D ii) Pain VRS iii) Complications iv) Residential status v) Subjective mobility status vi) Resource use vii) Routinely collected radiographs 	Participant or proxy & medical record and radiographs	Telephone, online or postal; medical record review
Yearly, up to 5 years post- diagnosis*	i) Mortality ii) Revision surgery iii) EQ-5D iv) Complications	i) & ii) Routinely collected hospital administrative databases (inpatient & emergency care); civil registers of deaths	i) & ii) NHS Digital, NHS Wales Informatics Service, Dept of Health (Northern Ireland) iii) Telephone, online or postal

Clinical Research Protocol Template version 15.0 CONFIDENTIAL

© Copyright: The University of Oxford and Oxford University Hospitals NHS Foundation Trust 2019 Page 19 of 27

		iii) Participant or proxy	
Event driven – reporting of a related admission to hospital*	i) EQ-5D	Participant or proxy	Telephone, online or postal

Table 1: Assessment schedule, instruments and means of collection.

*Key: *indicates measurement timepoint or data collected is in addition to the Platform Common Dataset specified in the master protocol*

9.6.2 Visits and Contacts

Contact 1: Details of the baseline contact are described in the Master Platform Protocol.

Contact 2: All participants will be invited for face to face or remote follow-up for a routine clinical checkup at approximately 6 weeks post-surgery. It is expected that approximately 60-70% of patients will be able to attend this appointment, with the remaining patients unable to as they are either still in a hospital setting or due to cognitive impairment and/or mobility. For those patients attending hospital a member of the local research team will perform the SPPB test with the patient and ask them to complete the required questionnaires. A 'mobile' research associate will visit those patients unable to attend, at their current place of residence to complete the SPPB test and questionnaires.

Contacts 3-8: Further follow-ups at 4, 12, 24, 36, 48 and 60 months post-diagnosis, will be completed with the participant or a proxy either via telephone interviews by a member of the central research team, or through electronic means depending on choice expressed by the participant or proxy at the time of consent/declaration. All de-identified routinely acquired radiographs up until 12 months will be collected and transferred to the central study team.

Event-driven contact: Reporting of an expected and related, local SAE (a related local complication - as defined in Section 10.1 of this appendix) by either the site staff, participant or proxy, will trigger collection of additional EQ-5D assessments. For participants yet to complete the first 4 months of data collection this will be a single additional EQ-5D report recorded by the site staff or participant/proxy as soon as possible after the event has been reported. For participants who have completed 4 months of data collection, this will be the index EQ-5D report (at the time of the event report) and two subsequent reports 4 and 8 weeks later.

9.7 Definition of End of Study

The end of comparison is the point at which the follow up of the last participant has been completed, all the data has been entered and all queries have been resolved. The last direct data collection will be at five years. The Sponsor and main Research Ethics Committee will be notified in writing within 15 days if the comparison has been concluded or terminated early.

